14.5 Patient Characteristics and significant protocol violations

Baseline subject characteristics will be tabulated, such as demographics (age, race, gender), and disease characteristics (ds-GPA).

14.6 Disposition

The reasons for patient treatment and study discontinuation will be summarized.

14.7 Analysis of Primary Objectives

For the primary objective of 6 month symptomatic radiation necrosis for dose-reduced stereotactic radiosurgery concomitant with immunotherapy, the proportion of patients who have symptomatic radiation necrosis at 6 months will be calculated using Kaplan-Meier method along with a 95% confidence interval. Testing the observed proportion smaller than a baseline 6 month symptomatic radiation necrosis rate of 16% at a type I error rate of 5% using a one-sided binomial exact test will be done.

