3. OBJECTIVE(S)

3.1 Primary Objective

To evaluate toxicity rates of brain metastasis after ICI concurrent with SRS at six months with regard to symptomatic radiation necrosis, defined as a 6-month rate of clinical symptomatology requiring steroid administration (i.e. Decadron), bevacizumab (Avastin), and/or operative intervention concomitant with advanced and routine brain imaging findings consistent with radiation necrosis.

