14.3 Analysis Datasets

Enrolled Population

The enrolled population comprises all subjects who meet the eligibility criteria and are registered onto the study.

Safety Population

The safety population comprises all subjects who have received at least one dose of radiation. This set will be used for safety analysis.

Efficacy Population

The efficacy population comprises all subjects who have completed stereotactic radiosurgery. This population will be used for efficacy analysis.

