14.4 Sample Size

An optimum one-stage design is planned. We specify a historical 6 month symptomatic radiation necrosis rate of 16% and an expected 6 month symptomatic radiation necrosis rate of 5%. Then, to achieve a power of 80% and control the type I error below 10%, a total of 40 patients evaluable for symptomatic radiation necrosis will be enrolled in the study. If at most 4 patients will experience symptomatic radiation necrosis in 6 months, the proposed dose reduction is claimed to be desirable. Otherwise, it is undesirable. We assume that at most 5% of the patients will not be evaluable for symptomatic radiation necrosis, which results in a total sample size of 42. In addition, we will add an interim analysis for the 6 month local control rate. When 20 patients have been enrolled in the study with their local control outcome being available, we will conduct a binomial exact test for the null hypothesis that the proposed method can maintain a 6 month local control rate of at least 75%. If p-value of this binomial test is less than 0.05, we will reject the null hypothesis and terminate this study earlier for futility.

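### 14.7 estimates 6-month symptomatic radiation necrosis by Kaplan-Meier and tests it by exact binomial without a rule for necrosis-free deaths; with 2 events the 5% test can turn on that rule

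*Combined protocol and SAP*

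**What the plan says.** Section 14.7 gives two analyses of the primary endpoint. The estimate: "the proportion of patients who have symptomatic radiation necrosis at 6 months will be calculated using Kaplan-Meier method along with a 95% confidence interval". The test: "Testing the observed proportion smaller than a baseline 6 month symptomatic radiation necrosis rate of 16% at a type I error rate of 5" per cent, one-sided and exact binomial. It states no censoring rule, no competing event and no denominator.

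Other sections touch on the denominator without fixing it:

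- Section 14.3 defines both analysis sets by radiation received: "The safety population comprises all subjects who have received at least one dose of radiation" and "The efficacy population comprises all subjects who have completed stereotactic radiosurgery". Neither excludes patients who die early.
- Section 14.4 plans on a different basis: "a total of 40 patients evaluable for symptomatic radiation necrosis will be enrolled in the study", and "We assume that at most 5% of the patients will not be evaluable for symptomatic radiation necrosis". It does not define evaluable. Its own decision rule is a count: "If at most 4 patients will experience symptomatic radiation necrosis in 6 months".
- Section 14.1 rules out imputation of missing data and does not mention deaths.
- The section on criteria for removal from study lists death among the reasons for early withdrawal, and 14.6 only summarises discontinuation reasons.
- Section 5.1 requires an estimated median survival of at least 6 months, so some deaths inside the 6-month window are foreseeable. The documents give no early-death rate for eligible patients.

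**The concern.** A patient who dies SRN-free at month 3 can no longer develop SRN. Kaplan-Meier with that death censored estimates the risk that would apply if nobody died first (a net risk). That is not the proportion of patients who have SRN (a crude risk), which is what 14.7 says it reports. One minus Kaplan-Meier is never below the crude proportion and exceeds it when SRN-free deaths precede SRN events.

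The exact test needs a whole-number denominator. An analyst following 14.3 keeps the early deaths in as patients without SRN. An analyst following 14.4 could treat a patient who died before the 6-month assessment as not evaluable and drop them. Both could claim to have followed the plan, in an unblinded single-arm study. At stake is whether the 5% test passes at the count nearest the planned rate.

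**Working it through.** **Inputs.** From 14.4: null rate 16%, expected rate 5%, 40 evaluable, 42 in total, at most 5% not evaluable. From 14.7: one-sided exact binomial test at 5%.

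**The plan's own figure.** The smallest n with P(X ≤ c | n, 0.16) < 0.10 and P(X ≤ c | n, 0.05) ≥ 0.80 is n = 40, with c = 3 (0.098 and 0.862). So 40 reproduces. 40/0.95 = 42.1, in line with the stated 42. The printed cutoff of 4 has a different error rate; that is a separate matter and is not used here.

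**Where the 5% test changes.** p = P(X ≤ x | n, 0.16), starting from 42 treated and removing SRN-free deaths:

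| SRN | p, deaths kept (n = 42) | Last n that passes | First n that fails | Deaths dropped to fail |
|---|---|---|---|---|
| 0 | 0.0007 | 18 (0.0434) | 17 (0.0516) | 25 (60%) |
| 1 | 0.0059 | 28 (0.0480) | 27 (0.0555) | 15 (36%) |
| 2 | 0.0266 | 38 (0.0448) | 37 (0.0509) | 5 (12%) |
| 3 | 0.0790 | none up to 42 | – | fails either way |

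Two SRN is the count nearest the planned rate (0.05 × 42 = 2.1). If only the planned two patients are lost, 2/40 gives p = 0.0345 and still passes.

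**How often the two denominators would disagree.** The documents do not give the survival figure, so this is an illustration only. Assume independent exponential hazards and a 5% net 6-month SRN risk: h = −ln(0.95)/6 for SRN and l = ln 2/m for death, with m the median survival in months. Then

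- crude SRN a = h/(h+l) × (1 − exp(−6(h+l)));
- SRN-free death d = l/(h+l) × (1 − exp(−6(h+l))).

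Summing the trinomial (SRN, SRN-free death, neither) exactly over 42 patients:

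| Assumed m | a | Kaplan-Meier minus crude (points) | Expected SRN-free deaths | Denominators disagree |
|---|---|---|---|---|
| 60 | 4.8% | 0.2 | 2.7 | 4% |
| 48 | 4.8% | 0.2 | 3.4 | 7% |
| 36 | 4.7% | 0.3 | 4.5 | 13% |
| 24 | 4.6% | 0.4 | 6.5 | 22% |
| 12 | 4.2% | 0.8 | 12.0 | 34% |

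At medians of 24 months or more, essentially all the disagreement comes from exactly 2 SRN. At 12 months, 27 of the 34 points come from 2 SRN and about 7 from 1 SRN. With every patient at the 6-month entry floor the estimator gap would be 1.4 points. That is a limit, not an expectation, because 5.1 sets 6 months as a minimum.

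**The case against.** The strongest reply is that 14.3 already settles the denominator. Section 3.1 frames the primary endpoint as toxicity ("To evaluate toxicity rates of brain metastasis after ICI concurrent with SRS at six months"), 14.3 assigns safety analyses to everyone who received radiation, and the efficacy set keeps early deaths too. *Evaluable* appears only in the sample-size section, and a patient who died SRN-free need not be missing. This has force: keeping deaths in is the more natural reading. It does not close the point, because 14.7 names no population and 14.4 counts the patients for this endpoint as evaluable ones.

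Second, nothing changes inside the plan's own 5% allowance. That is correct. But the allowance is an assumption, and it can be relied on only once the plan says whether deaths fall within it.

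Third, the go/no-go rule in 14.4 is a raw count and does not depend on the denominator. That stands in full.

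Fourth, the estimator gap is small, and a net risk is a legitimate target. The size is conceded. But 14.7 describes a proportion of patients, and a net risk is not that.

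A reader might also infer that the primary test is generally unreliable at 0, 1 or 2 SRN. The documents do not support that. Reversal at 0 SRN needs 25 SRN-free deaths of 42, more than the 20.5 expected on the model above even at the entry floor. At 1 SRN it needs 15.

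**Conclusion.** The concern holds in a limited form. Two things are established from the documents alone: 14.7 pairs a Kaplan-Meier estimate with a quantity that Kaplan-Meier overstates once SRN-free deaths are censored, and it leaves the binomial denominator open. The consequence for the 5% test is concentrated at 2 SRN, where dropping five or more deaths turns p = 0.027 into p = 0.051 or higher. It reaches 1 SRN only with heavy early mortality.

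The frequency of disagreement, about 4% to 34% for assumed medians of 60 to 12 months, rests on exponential, independent hazards and on survival figures that the documents do not supply. It should not be read as a forecast. Nor should a reader conclude that the dose-reduction decision in 14.4 is in doubt on this ground, or that the reported rate would be seriously wrong. This should be fixed before outcomes are analysed, because the remedy is cheap and the choice should not be made with the data in view.

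**What to change.** In 14.7, name the 14.3 population and estimate 6-month SRN by Aalen-Johansen cumulative incidence, with SRN-free death as a competing event. Run the exact test on treated patients with known 6-month status, counting SRN-free death before 6 months as a known non-event. In 14.4, define evaluable to match, so that the 5% covers only loss to follow-up or missing imaging. Report the number of early deaths beside the result, with a deaths-dropped analysis as sensitivity. State that a small difference between estimate and test remains for patients lost to follow-up; the passing count stays at 2 for every n from 38 to 42, so the planned loss of two does not move it.

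The cost is wording and one standard routine, with no extra patients. The real downside is that more deaths make the test easier to pass. Whether that matters depends on the 16%. The background gives its source range, 12% to 20%, as a share of treated patients, which suggests a crude rate; the sponsor should confirm this and that it refers to 6 months, or re-base it. If it is crude, the chance of passing under the null with 42 patients is 2.7%. If it is net, the same model with a 16% net risk gives a = 14.7% or 13.6% and P(X ≤ 2 | 42, a) = 4.2% or 6.3% at assumed medians of 24 or 12 months, so the 5% level could be exceeded.

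Dropping deaths avoids that (1.5% or 1.3% under the same net null). But at a 5% net risk it cuts the chance of passing from 70% to 47% (24 months) or from 74% to 40% (12 months). That is why it is better kept as a sensitivity analysis.

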14.8 Analysis of Secondary Objectives

For the secondary objectives of 6-month local control, 6-month radiographic radiation necrosis, 12-month symptomatic radiation necrosis, 12-month local control, 12-month radiographic radiation necrosis and 12-month local control rate by SRS modality, Kaplan-Meier methods will be used to provide point estimate with 95% confidence intervals. The method of Klein et al., (Klein et.al., 2007) will be conducted for the group comparison.

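### The primary Kaplan-Meier 95% interval is of unstated type: its usual forms give no usable interval at 0 events, and at 1 to 3 events agreement with the planned exact test depends on the software default

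*Combined protocol and SAP*

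**What the plan says.** Section 14.7 (Analysis of Primary Objectives) asks for two things. The SRN proportion at 6 months "will be calculated using Kaplan-Meier method along with a 95% confidence interval". It is then tested for being below 16% "at a type I error rate of 5% using a one-sided binomial exact test". The section does not say how the interval is built, what to report if no event occurs, or how a reader should treat an interval and a test that point different ways.

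Section 14.4 (Sample Size) gives the design values: "We specify a historical 6 month symptomatic radiation necrosis rate of 16" per cent, "an expected 6 month symptomatic radiation necrosis rate of 5" per cent, and the aim "to achieve a power of 80% and control the type I error below 10" per cent. From these, "a total of 40 patients evaluable for symptomatic radiation necrosis will be enrolled in the study". It also sets a count rule: "If at most 4 patients will experience symptomatic radiation necrosis in 6 months, the proposed dose reduction is claimed to be desirable".

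Section 14.8 uses the same unspecified form for the secondary endpoints: "Kaplan-Meier methods will be used to provide point estimate with 95% confidence intervals".

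**The concern.** The design expects 40 × 0.05 = 2 events. Standard Kaplan-Meier output uses the Greenwood variance with a large-sample normal approximation, and that approximation is weak at such counts. With no event the estimated variance is zero. With 1 to 3 events the common transformations give quite different upper limits, and 16% lies between them.

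Readers will compare the upper limit of the primary interval with 16%. If the form is left to the software, the published interval may appear to contradict the test in either direction. The form could also be picked after the data are known. In the most favourable outcome, no events at all, the primary estimate would have no usable interval.

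**Working it through.** **Inputs.** From section 14.4: n = 40 evaluable, null rate 16%, expected rate 5%, type I error below 10%, power 80%, cut-off at most 4. From section 14.7: one-sided exact test at 5%, Kaplan-Meier 95% interval. Assumption: nobody is censored before 6 months, so the Kaplan-Meier estimate is k/40. The documents do not give the amount of censoring; n = 38 and n = 42 are checked below.

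**The plan's own figure.** With X ~ Binomial(n, p), a search over n = 30 to 45 for P(X ≤ r | 0.16) ≤ 0.10 and P(X ≤ r | 0.05) ≥ 0.80 gives n = 40 as the smallest, with r = 3 (type I error 9.8%, power 86.2%). So 40 reproduces, and 40 × 1.05 = 42. The printed cut-off r = 4 gives type I error 21.1% and power 95.2%. The 5% test is met at r = 2 (type I error 3.5%, power 67.7%).

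**Formulas.** S = 1 − k/40; se = √[S(1 − S)/40], which is Greenwood without censoring; z = 1.96.
- Plain upper limit: k/40 + z·se
- Log: 1 − S·exp(−z·se/S)
- Log-log: 1 − S^exp(z·s), with s = se/(S·|ln S|)
- Exact upper limit: the p that solves P(X ≤ k | p) = a, with a = 0.025 for the two-sided 95% interval and a = 0.05 for the one-sided 95% bound

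Examples:
- 3/40, plain: 0.075 + 1.96 × 0.0416 = 15.7%.
- 3/40, log: 1 − 0.925·exp(−1.96 × 0.0450) = 15.3%.
- 2/40, log-log: s = 0.0363/0.0513 = 0.707, exp(1.96 × 0.707) = 4.00, and 1 − 0.95^4.00 = 18.5%.

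**Upper limits (%), n = 40**

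| Events | P at true 5% | Exact p vs 16% | Plain | Log | Log-log | Exact two-sided 95% | Exact one-sided 95% |
|---|---|---|---|---|---|---|---|
| 0 | 12.9% | 0.0009 | 0 (zero width) | 0 (zero width) | undefined | 8.8 | 7.2 |
| 1 | 27.1% | 0.008 | 7.3 | 7.2 | **16.5** | 13.2 | 11.3 |
| 2 | 27.8% | 0.035 | 11.8 | 11.5 | **18.5** | **16.9** | 14.9 |
| 3 | 18.5% | 0.098 | **15.7** | **15.3** | 21.5 | 20.4 | 18.3 |
| 4 | 9.0% | 0.211 | 19.3 | 18.8 | 24.5 | 23.7 | 21.4 |

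Bold marks disagreement with the 5% test. At a true 5%, the log-log conflict (1 or 2 events) has probability 27.1 + 27.8 = 54.8% (from unrounded values), and the plain and log conflict (3 events) 18.5%. The plain lower limit is negative at 1 to 3 events (−2.3, −1.8, −0.7%). The log lower limit is truncated at 0. Log-log stays within 0 to 100%.

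**Coverage, n = 40, zero-event trials counted as misses**

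| True rate | Plain | Log | Log-log | Exact 95% |
|---|---|---|---|---|
| 5% | 86.8% | 87.1% | 82.3% | 98.6% |
| 8% | 83.7% | 83.7% | 92.7% | 98.7% |
| 16% | 89.4% | 89.4% | 95.4% | 97.3% |

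At a true 5% the shortfall is almost all the zero-event case. Adding back its 12.9% gives about 99.7, 99.9 and 95.2%. At 8% the zero-event probability is 0.92^40 = 3.6%, so plain and log still reach only about 87.2%. At 16% zero events are negligible. The plain and log shortfall is then mostly P(X ≤ 3 | 0.16) = 9.8%, since their upper limits lie below 16% at 0 to 3 events.

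**Sensitivity to n.** At n = 42, plain and log still conflict at 3 events (14.9% and 14.6%, p = 0.079), and log-log only at 2. At n = 38, plain and log do not conflict at any count, while log-log conflicts at 1 and 2.

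**The case against.** The plan does not prescribe Greenwood or any transformation; an exact-type Kaplan-Meier interval would satisfy section 14.7 as worded. The decision rests with the exact test and the event cut-off, and nothing makes the interval a decision rule. A two-sided 95% interval beside a one-sided 5% test is common reporting practice, and the resulting mismatch is not peculiar to Kaplan-Meier: the exact 95% interval also disagrees at 2/40. The 3/40 conflict exists only if the 5% test governs. At the 10% level of section 14.4, p = 0.098 passes and the plain and log limits agree with it.

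All of this stands, and it limits the point. A reader might infer that the interval fails throughout 0 to 3 events, that its coverage at the expected rate is really 82 to 87%, or that the primary interval is wrong as written. The documents do not support those readings. Only the plain form leaves the 0 to 100% range at 1 to 3 events, the low coverage at a true 5% comes almost entirely from the zero-event trials, and the text leaves the form open rather than choosing a bad one.

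What the objection does not remove is the missing zero-event rule and the dependence on the software default. The log-log conflict at 1/40 and 2/40 holds under the 5% test, the 10% level and the cut-off of 4 alike.

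**Conclusion.** The point holds as a gap in specification. Ordinary Kaplan-Meier output, which section 14.7 permits, gives no usable primary interval at 0 events. At n = 40 each of the plain, log and log-log forms disagrees with the 5% exact test at some count from 1 to 3. Plain and log also under-cover at some true rates (about 84% at 8% and 89% at 16%); log-log is near nominal apart from the zero-event case. Part of the disagreement is the pairing of a two-sided 95% interval with a one-sided 5% test.

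These figures assume 40 evaluable patients and no censoring before 6 months. With censoring, the Kaplan-Meier estimate and the binomial proportion would themselves differ. The larger inconsistency between at most 2 events (5% test), at most 3 (10% level) and at most 4 (printed cut-off) is a separate matter, but it must be settled first because it fixes the level that the interval should match.

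**What to change.** 1. Reconcile the 5% test in section 14.7 with the 10% level and the at-most-4 cut-off in section 14.4, and state which rule governs.
2. In section 14.7, report the event count with a Clopper-Pearson interval whose one-sided upper bound matches that rule. For the 5% test this is the two-sided 90% interval, with upper limits 7.2, 11.3, 14.9 and 18.3% for 0, 1, 2 and 3 of 40. These are below 16% exactly when p < 0.05. For a 10% test use the one-sided 90% bound: 5.6, 9.4, 12.8, 15.9 and 19.0% for 0 to 4 events, which matches a cut-off of 3. If the cut-off of 4 were kept, neither bound would agree with it at 4/40.
3. Show the exact two-sided 95% interval alongside, so that the planned level is still reported, and label which interval corresponds to the test.
4. If patients are censored before 6 months, use an exact-type interval for the Kaplan-Meier estimate (beta product confidence procedure).
5. Consider the same wording in section 14.8 for radiographic necrosis when events are few.

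Cost: wording only, with no added patients or data. The matched exact interval has higher upper limits than plain or log (14.9% against 11.8% and 11.5% at 2/40), but lower ones than log-log at 1 to 3 events.

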14.8 Analysis of Secondary Objectives

For the secondary objectives of 6-month local control, 6-month radiographic radiation necrosis, 12-month symptomatic radiation necrosis, 12-month local control, 12-month radiographic radiation necrosis and 12-month local control rate by SRS modality, Kaplan-Meier methods will be used to provide point estimate with 95% confidence intervals. The method of Klein et al., (Klein et.al., 2007) will be conducted for the group comparison.

14. MULTICENTER GUIDELINES

15.1 Study Documents

Each participating site must submit regulatory documents (informed consents, 1572s, Financial Disclosures, IRB approval documents, Continuing Reviews, Amendments, patient brochures or recruitment material etc.) to the Coordinating Center. The Coordinating Center will provide each site with a comprehensive list of the required documents prior to study start-up, throughout the duration of the study and upon study close-out. It is the responsibility of the participating site to maintain copies of all documentation sent to the Coordinating Center.

15.2 Study Initiation

Before activating the clinical trial at each participating site, the IUSCCC CTO Multicenter Clinical Research Coordinator, or designee, will ensure that:

- Full **Institutional Review Board (IRB) approval** has been obtained.
- Research staff at the participating site has been trained in data entry into *OnCore*®
- A **start-up meeting** with each institution has taken place via telephone conference. The start-up meeting will cover protocol details (including eligibility criteria, treatment plan, etc.), responsibilities of the participating investigators, and reporting procedures.
- A financial **conflict of interest statement** from each investigator has been obtained.

15.3 Patient Enrollment

After eligibility is confirmed by the participating site staff, a completed eligibility checklist, supporting source documentation, and signed consent will be sent to IUSCCC for verification. The Multicenter Clinical Research Coordinator, or designee, will assign the patient a study number and return the enrollment information to the site. The site staff will then register the patient in *OnCore*®. *Additional details of this process can be found in the Study Procedure Manual.*

15.4 Data Monitoring

All multicenter investigator initiated trials conducted at the IUSCCC are subject to data monitoring by the Multicenter Clinical Research Coordinator and the IUSCCC Compliance Office, or designee. External sites will be notified of upcoming monitoring visits and will be expected to provide the Multicenter Clinical Research Coordinator, IUSCCC Compliance Office, or designee, with de-identified source documents for remote monitoring of patients. Queries will be issued in OnCore® and a detailed monitoring report will be provided to the participating site. The IUSCCC will also forward any monitoring and/or auditing reports to the DSMC.

When a patient enrolled on this trial, or the trial itself, is selected for local monitoring or auditing, the participating site will forward the results to the Multicenter Clinical Research Coordinator, or designee. In addition, if a participating site patient is selected for local auditing by the IUSCCC DSMC, the site will be responsible for sending IUSCCC de-identified source documents.

